Appendix 4 – Caregiver Survey (Phase 2 Secondary Aim #2)

Part One

Thank you for agreeing to participate in this study of pain scales used in children. Your responses will help us make sure we are doing the best job we can to address your child's pain. Please do not ask your child about his/her pain while you answer these questions.

What do you believe is hurting on your child?

These faces show how much something can hurt. The face on the far-left shows no pain. The faces show more and more pain up to the far-right. It shows very much pain.

Please circle the face that shows how much you think your child hurts right now.

Each face below is for a person who has no pain, or some, or a lot of pain. Face 0 doesn't hurt at all. Face 2 hurts just a little bit. Face 4 hurts a little bit more. Face 6 hurts even more. Face 8 hurts a whole lot. Face 10 hurts as much as you can imagine, although you don't have to be crying to have this worst pain.

Please circle the face that represents your child's pain right now.

Part Two

Your child has received medications to help lessen his/her pain. Please answer the following questions about your child and his/her level of pain right now.

Please do not ask your child about his/her pain while you answer these questions.

These faces show how much something can hurt. The face on the far-left shows no pain. The faces show more and more pain up to the far-right. It shows very much pain.

Please circle the face that shows how much you think your child hurts right now.

Each face below is for a person who has no pain, or some, or a lot of pain. Face 0 doesn't hurt at all. Face 2 hurts just a little bit. Face 4 hurts a little bit more. Face 6 hurts even more. Face 8 hurts a whole lot. Face 10 hurts as much as you can imagine, although you don't have to be crying to have this worst pain.

Please circle the face that represents your child's pain right now.

Do you think your child is in less pain than when you last rated his/her pain in Part One? (Circle your answer)

Yes No

If yes, what makes you believe his/her pain is less`?

If no, what makes you think his/her pain is not less?

Part Three

If you do not feel that your child's pain has improved, please notify a provider at this time.

Please answer the following questions about your child's ability to report his/her pain.

Do you think that your child would understand the pain scales you used to rate his/her pain?

(Circle your answer)

Yes No

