Pediatric Pain Assessment in the Emergency Department

NCT03157882

October 13, 2017

Primary Investigator:

[name] Pediatric Emergency Medicine Fellow Department of Emergency Medicine Division of Pediatric Emergency Medicine [name]

Co-Investigators:

[name] Department of Emergency Medicine Division of Pediatric Emergency Medicine [name] [contact]

[name] Research Director Department of Emergency Medicine [name] [contact]

[name], CCRA Department of Emergency Medicine [name] [contact]

[name] [name], MSPH Director of Research in Biostatistics Dickson Advanced Analytics [name] [contact]

Purpose:

To examine how pediatric pain scales are used in clinical practice in a pediatric emergency department (ED). Specifically we will examine the use of Wong-Baker FACES ® Pain Rating Scale (WBF) and Faces Pain Scale – Revised (FPS-R) by ED nurses, as well as the correlation of results with the children's subjective descriptions of pain before and after an analgesic intervention as well as parental estimates of their children's pain. We will determine if a child's successful use of these scales can be predicted by evaluating his/her neurocognitive development.

Background:

"Most children five years and older can provide meaningful self-reports of pain if they are provided with age appropriate tools and training."¹ Self-report is the desired method of data collection.^{2,3} Face scales provide an ordinal self-report of pain, and the literature suggests that they are the preferred method of pain reporting by children.²

Both the WBF and the FPS-R have been studied extensively in children with chronic pain, postoperatively, and those experiencing procedural pain; however, data for their use in assessing acute pain while in the ED is limited. It is imperative that pain be assessed accurately, as it is the most common reason for presentation to the ED. However, it is also important because often we draw conclusions about the efficacy of an intervention based on the results of these pain scales.

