Exclusion criteria

Altered mental status History of traumatic brain injury (TBI) History of developmental delay History of Autism History of chronic pain, defined as persistent or recurrent pain in children with chronic health conditions⁸ Non-verbal patients

Outcome Measures:

Phase 1 - Primary Aim

Rate of intended script use in pain scale delivery Review of themes during nursing pain assessment Consistency in delivery of WBF by nursing

Phase 2 - Primary

Neurocognitive development score BRIGANCE ® score Initial WBF score Repeat WBF score Initial FPS-R score Repeat FPS-R score Anchor report of pain (a lot better, a little better, the same, a little worse, a lot worse)

Phase 2 - Secondary

Initial WBF score (patient and caregiver) Repeat WBF score (patient and caregiver) Initial FPS-R score (patient and caregiver) Repeat FPS-R score (patient and caregiver)

Study Definitions:

"Caregiver" will refer to an adult who is able to provide consent for treatment and provides regular care for the child.

"Chronic pain" includes persistent (ongoing) and recurrent (episodic) pain in children with chronic health conditions.

Convergent validity evaluates the degree to which two different scales that are supposed to measure the same thing produce similar results.

"Repeat pain score" will be completed approximately 20 minutes after the initial pain score, or if administered, approximately 20 minutes after analgesic intervention.

Responsivity is the degree to which a test behaves in a manner that is consistent with what the test is purported to measure. It determines whether the measure is able to identify changes in pain over time that are clinically important to patients.

Phase 1 Study Protocol:

- 1. Once the subject is identified, the caregiver will provide verbal consent for participation in the study.
- 2. After verbal consent is obtained, the primary investigator will observe and audio record nursing's assessment of the patient's pain and complete the observation checklist (Appendix 1).

Phase 2 Study Protocol:

- 1. Once the subject is identified, the caregiver will provide written consent for participation in the study (if a self-report pain score was not collected in the triage process, patients with pain or a potentially painful condition will have their pain assessed using an age appropriate self-report pain scale by the PI or designee).

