- 2. Early in the ED visit, the investigator or designee will help the patient complete Part One of the Patient Survey (Appendix 3), which includes the WBF, and the FPS-R.
- 3. The caregiver will also complete Part One of the Caregiver Survey (Appendix 4).
- 4. Subjects will be treated per usual care by an MD/ACP.
- 5. The investigator or designee will help the patient complete Part Two of the Patient Survey (Appendix 3), which includes the WBF and the FPS-R. This will occur approximately 20 minutes after analgesic administration, if it was ordered.
- 6. The caregiver will also complete Parts Two and Three of the Caregiver Survey (Appendix 4).
- 8. If the patient indicates that he/she feels the same or worse on Part Two of the Patient Survey the treating MD/ACP will be notified.
- 9. The patient will be reassessed by the PI or designee at least 20 minutes after analgesic administration, if it was ordered, or after a reasonable time period if no analgesic medication was ordered.
- 10. On reassessment, if the patient says that he/she is willing to participate, the PI or designee will complete a brief neurocognitive skills assessment (Appendix 2) as well as the BRIGANCE ® Early Childhood Screens III with the patient. If the patient is not willing to participate, study assessments will cease.

Statistical Analysis:

Phase 1

Sample size: 30

Rate of compliance with intended script and rate of consideration of caregiver perception will be reported as percentages. Qualitative data will also be reviewed by the PI for the emergence of themes.

Phase 2

Sample size: approximately 250

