Responsivity will be measured by correlating the change in the WBF and FPS-R scores before and after analgesic intervention with the anchor change in pain score (a lot better, a little better, the same, a little worse, a lot worse). Pearson correlations will be estimated between each change score and the anchor score. In addition, we will use ANOVA to test the difference in mean pain change among the children reporting "a lot better", "a little better", and "the same". For the scales to be considered responsive, we would need to see significant reductions for the children reporting "a lot better", minimal to no reduction for those reporting "the same", and increase in pain for those reporting "worse". We will need a relatively large number of children in each category (a lot better, a little better, the same) to be able to test for differences (at least 30 per group). We will use Fisher's z-transformation to test if level of neurocognitive development impacts responsivity. Levels of neurocognitive development will be defined as at or above expected or lower than expected. The Fisher's z-transformation formally tests if the correlations between two measures (change in pain and anchor rating) differ between two groups. Here we assume we will have significant variability in change scores and in the anchor ratings to conduct these correlations and the formal test. We would need at least 56 children in each neurogcognitive development group (expected or above versus below). If the variability is limited in that most children report improvement and few report same or worsening, we will test for responsivity differences using a two-way ANOVA where the two factors are self reported anchor response ("better", "same" or "worse) and neurocognitive level (expected or above expected vs below expected). The outcomes are the change in the WBF and the change in the FPS-R. The test of interest will be the two way interaction between the anchor and the neurocognitive development level. The BRIGANCE also provides the developmental age for each child which can be compared to their actual age. We will test if this difference is significant using a paired t-test. We will also explore the age where responsivity worsens by conducting similar analyses but stratified by actual age (each year) and developmental age. Given the proposed analysis, we will need at least 50 children for each cognitive age (3, 4, 5, 6, and 7 years) assuming at least 10 fall into the "a lot better", "a little better", "the same" categories for the anchor pain question.

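### Part Two of the Caregiver Survey tells every caregiver that the child has had pain medication, although the protocol foresees children who have had none

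*Combined protocol and SAP*

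**What the plan says.** Appendix 4 contains one caregiver form. Its Part Two begins "Your child has received medications to help lessen his/her pain", with no condition, skip rule or second version. Answering instructions and scale text follow, then the two repeat face ratings.

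The protocol treats analgesia as something that may or may not happen:
- Study Definitions time the repeat score "approximately 20 minutes after the initial pain score, or if administered, approximately 20 minutes after analgesic intervention".
- Phase 2 Study Protocol, step 4: "Subjects will be treated per usual care by an MD/ACP".
- Step 5, on the child's second survey: "This will occur approximately 20 minutes after analgesic administration, if it was ordered".
- Step 6: "The caregiver will also complete Parts Two and Three of the Caregiver Survey (Appendix 4"), with no exception for untreated children.
- Step 9 provides for reassessment "or after a reasonable time period if no analgesic medication was ordered".

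The Phase 2 inclusion criteria require a pain score of at least 4/10 but not an analgesic. Secondary Aim #2 compares initial and repeat child and caregiver ratings in children with acute pain, without limiting this to treated children. The Statistical Analysis section uses ICCs at matching time points.

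Other text reads as if every child is treated. The Purpose speaks of "subjective descriptions of pain before and after an analgesic intervention", the analysis section says "Responsivity will be measured by correlating the change in the WBF and FPS-R scores before and after analgesic intervention", and the convergent-validity paragraph uses the same framing.

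**The concern.** Followed as written, the plan gives some caregivers an untrue statement immediately before they produce an endpoint rating. A caregiver told that pain relief has been given might expect less pain and rate accordingly. Part One carries no such statement, so the caregiver ratings at the two time points are also collected under different framing.

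What is at stake is the repeat-time-point ICC in Secondary Aim #2. Behind the form lies a wider inconsistency. The conditional branch in the Study Definitions and protocol steps does not fit the all-treated wording in the Purpose and Statistical Analysis. The reader cannot tell whether untreated children enter the responsivity and convergent-validity analyses.

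**Working it through.** **Text comparison.** No calculation is needed for the contradiction.
1. The form asserts medication for every child.
2. The repeat-score definition has a branch in which no analgesic is given. That definition governs the repeat score itself, so reading step 9 as a separate, later reassessment does not remove the conflict.
3. Step 6 does not exempt the untreated branch from Part Two.
4. The repeat ratings enter an ICC for a population not restricted to treated children.

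**Possible size.** The plan gives no figure to reproduce. Only the 0-10 face scale in steps of 2 and the approximate sample size of 250 come from the documents; every other input is assumed.

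Let a fraction p of caregivers shift down by δ points. Let d be the mean by which caregivers rate above children when there is no shift, V the sum of the child and caregiver variances, and C their covariance. On a continuous scale:
- Absolute-agreement ICC = 2C / (V + d²) without the shift.
- The shift adds p(1-p)δ² to the caregiver variance and changes the mean difference to d - pδ. The denominator therefore becomes V + d² + pδ(δ - 2d).
- The ICC falls if d < δ/2, is unchanged if d = δ/2, and rises if d > δ/2.

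Example with assumed SDs of 2.3 (true pain), 1.6 (child error) and 2.1 (caregiver error), and δ = 2:
- C = 2.3² = 5.29, so 2C = 10.58. V = (5.29 + 2.56) + (5.29 + 4.41) = 17.55.
- d = 0: 10.58/17.55 = 0.603. At p = 10%, 10.58/17.95 = 0.589 (change -0.013). At p = 60%, 10.58/19.95 = 0.530 (change -0.073).
- d = 2: 10.58/21.55 = 0.491. At p = 10%, 10.58/21.15 = 0.500 (change +0.009). At p = 60%, 10.58/19.15 = 0.552 (change +0.061).
- Consistency ICC, which ignores mean differences, at p = 60%: 10.58/(17.55 + 0.96) = 0.572 (change -0.031), under half the absolute-agreement fall.

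Simulation on the actual face scale (1,000,000 pairs per scenario, mean 5) used three sets of SDs for true pain / child error / caregiver error: 1.9/2.0/2.6, 2.3/1.6/2.1 and 3.0/1.3/2.0. With equal means these give ICCs of 0.38, 0.57 and 0.72. Changes in the absolute-agreement ICC for a 2-point shift were:

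| Untreated | Equal means (d = 0) | Caregivers 2 points higher (d = 2) |
|---|---|---|
| 10% | -0.008 to -0.012 | +0.006 to +0.010 |
| 60% | -0.043 to -0.068 | +0.040 to +0.063 |

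With caregivers 1 point higher the change is about 0, as the formula predicts. With a consistency ICC and equal means the fall at 60% is about 0.020-0.033. With no untreated children, or no shift, the change is 0.

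For scale, the sampling error of an ICC from 250 children (Fisher z, SE = 1/√(250 - 1.5) = 0.063) gives a 95% half-width of about 0.06-0.11 over these ICC values.

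**The case against.** The strongest defence is that the study is framed around an analgesic, so the form may simply describe the intended population. The form does agree with the Purpose and Statistical Analysis. But this relocates the conflict without resolving it, because the Study Definitions and steps 5 and 9 expressly provide for children without an analgesic.

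It is also fair to say that few children with pain of at least 4/10 may go untreated, that staff may correct the sentence aloud, and that caregivers present at the bedside may know it is wrong. The documents neither state nor exclude any of this. It limits the likely effect but does not make the sentence true.

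Stronger readings that a reader might infer are not supported:
- **That the sentence lowers the ICC and so favours the hypothesis of low reliability.** The sign depends on the caregiver-child mean difference, which is not given, and the documents set no threshold for low reliability.
- **That the sentence contaminates the primary aims.** It appears only on the caregiver form, while the primary aims use the child's own reports.
- **That the plan wrongly lets caregivers learn the child's answer.** Parts One and Two tell caregivers not to ask the child. The available text goes from step 6 to step 8 and does not say who is present, so a missing safeguard cannot be asserted.

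**Conclusion.** The contradiction holds on the text alone and with high confidence: the statement on the form is false for any untreated child, and it precedes ratings used in a secondary analysis. Its consequence is confined to the repeat caregiver ratings. Size and direction are unknown. The ranges of about -0.01 to +0.01 at 10% untreated and -0.07 to +0.06 at 60% rest on assumed SDs, an assumed 2-point shift in every affected caregiver, assumed mean differences of 0 to 2 points, and an absolute-agreement ICC that the plan does not specify. At a low untreated share the effect would be well inside sampling error. No changed conclusion can be shown. Severity is minor.

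**What to change.** 1. Delete the medication sentence from Part Two. The sentence after it only asks for answers about the child's present pain, so it suits every child and can open the section. The cost is a one-sentence form amendment.
2. Reconcile the all-treated wording in the Purpose and Statistical Analysis with the untreated branch in the Study Definitions and steps 5 and 9. State whether those analyses use the initial and repeat scores of all children or of treated children only. This needs a sentence or two in the analysis section.
3. Optionally, report the repeat ICC by analgesic status, using the medication and time fields already on the Patient Survey (Appendix 3). Label it descriptive, claim no power, and show blank fields as not recorded, because a blank cannot separate an untreated child from a missing entry. The report will be incomplete to that extent.

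The order of the surveys and the timing of Part Three should stay as they are. Having caregivers rate first could expose the child's self-report, which serves the primary aims, to the caregiver's rating. Holding back Part Three could delay its prompt to notify a provider.
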